#### 4.14 Initial Results from EIMG Implementation

From launch in 2016, EIMG expanded to 18 Prisma Health practices and six community PA facilities across Greenville County by 2019. Over time, referral numbers have been consistent within a clinic, demonstrating initial sustainability of the EIMG model. Yet, large variations exist in referral patterns between participating clinics.

As of the end of 2022, a total of 1471 patients had been correctly referred to the EIMG Referral Team (Figure 4) with 520 enrolling in the PA programs. Variation in referral patterns between clinics, as well as system level gaps in connecting patients to the PA programs, provides substantial rationale for investigating strategies to optimize the clinical implementation of the EIMG model.

Patients enrolled in the PA program graduated at rates of 48%, 63%, and 68% in 2016 through 2018, with a projected 72% in 2019/2020 (prior to shut down during coronavirus pandemic).

Analysis of a subgroup of patients (n=173) demonstrated a significant decrease in bodyweight (1.5±4.1 kg, p<0.001). Patients referred for hypertension (n=106), lost an average of 1.2±3.8 kg (p=0.002) and decreased their systolic (n=100) and diastolic blood pressure by 7±15 (p<0.001) and 3±8 mmHg (p=0.001), respectively. In an exit survey (n=153 graduates), all program components received high satisfaction scores (5-point Likert scale, 5 = "highly satisfied"). All provider ratings were above 4.75 and all satisfaction scores were above 4.9.

Despite the existence of a standardized framework for integrating EIM in Prisma Health clinics, variability in implementation fidelity has emerged over the initial years of the EIMG program. This underscores the need to understand the contextual factors and processes at both clinic- and provider-levels to enhance implementation of the EIMG model.

Figure 4. Results for EIMG clinic-to-community referrals, 2016-22.

Number of Correct Patient Referrals	Referrals to Community PA Centers	Patients Enrolled in PA Program	Patient Graduation (2016-19)
1471	1049	520	273
	71.3% referred patients connected to nurse navigator	35.4% of referred patients enrolled in a PA program	18.6% of referred patients graduated from a PA program
52.5% of enrolled patients graduated (273/520)			

## 5.0 STUDY OBJECTIVES

### 5.1 Primary Objectives

*Primary Aim.* To determine differences in clinic- and provider-level adoption (i.e., proportion and characteristics of clinics that adopt and initiate use of EIMG), implementation (i.e., delivery fidelity), and reach (i.e., number, proportion, and representativeness of patients) before and after EIMG integration at newly adopting Prisma Health primary care clinics.

### 5.2 Secondary Objectives

*Secondary Aim 1.* To assess the effectiveness of participating in the evidence-informed, 12-week PA program at the community PA facilities on patient health outcomes (i.e., body weight, blood pressure, hemoglobin A1c, lipid profiles) captured in their electronic health records.

*Secondary Aim 2.* To evaluate, from a health system perspective, the cost of implementing EIMG to estimate the effort of EIMG vs. standard care on costs and outcomes (effectiveness). We will use these estimates to obtain the incremental cost-effectiveness of EIMG vs. standard of care.

### 5.3 Significance to the Field

The completion of this study and achievement of our study aims has the potential to significantly advance understanding of how to optimally integrate a PA referral pathway into clinical settings that involves the prescription, referral, and engagement of patients in community-based PA programs. This study will enhance the operationalization of future large-scale, PA models in health systems that have diverse policies, practices, and patients. Study findings and resources will be made available to health systems for broad scale up with the goal of increasing patient engagement in community-based PA programs as an extension of healthcare systems. Finally, the achievement of our study aims will provide an economic evaluation that has the potential to impact coverage decisions made by insurance companies and adoption/implementation decisions made by health systems when determining the design and uptake of clinical/community health promotion programs.

## 6.0 STUDY DESIGN

### 6.1 Overview of Study Design

This study will employ a single arm, multiple case study design using a mixed methods approach to examine the adoption, implementation, and reach of EIMG across Prisma Health primary care clinics (i.e., clinic workflow, referral process), leading to patient enrollment in a community-based, evidence-informed PA program. Eligible Prisma Health primary care clinics that have not yet received EIMG onboard training and activation will be provided with the opportunity to adopt EIMG as a part of their clinic practice and patient workflow process. A mixed methods approach will examine contextual factors influencing decisions to adopt/not adopt EIMG.

Clinic champions at clinics adopting EIMG will be provided with a brief pre-recorded training video to disseminate to their clinic staff (e.g., physicians, nurses, medical assistants, administrative assistants) on how to provide their patients with an EIMG referral. All providers at the clinic will have the ability to screen and identify physically inactive patients and provide them with an EIMG referral. Initial implementation and reach of EIMG at adopting clinics will be tracked for approximately four months following the dissemination of the pre-recorded training video. After four months, the EIMG team will provide a more in-depth, standardized clinic onboard training following established protocols iteratively developed and refined through the initial addition of EIMG clinics between 2016-19. The onboard training, which consists of an overall presentation of the EIMG program and specific information on placing the referral order and patient workflow, has been adapted for virtual environments due to its notable added benefits, including its recording to serve as an ongoing reference tool for those who cannot attend initial training and incoming staff. Implementation and reach of EIMG will be tracked for an additional four months after the onboard training.

Referred patients will have the opportunity to enroll in an evidence-informed, 12-week PA program at local community PA facilities (e.g., YMCAs) that partner with EIMG. Upon enrollment and at the completion of the 12-week PA program, patients will undergo an assessment battery that includes the completion of a patient health questionnaire, anthropometric assessments (i.e., height, weight, waist circumference) and an evaluation of their mental and emotional health (i.e., PROMIS tool, PHQ-9). The RE-AIM framework will inform the assessment of implementation outcomes (i.e., adoption, implementation, and reach), while the i-PARIHS framework will be used to examine contextual factors (i.e., determinants) influencing clinic level outcomes. Patient demographics, health outcomes, healthcare utilization and costs of eligible patients at participating primary care clinics, both before and after EIMG onboarding, will be extracted from the Prisma Health EHR. Data will be compared between patients that receive EIMG referrals and matched controls at clinics that do not adopt EIMG: 1) the impact of EIMG on changes in health outcomes, and 2) the impact of EIMG on healthcare costs. These estimates will be used as the basis for cost-effectiveness analyses of EIMG and serve as the foundation for long-term evaluation modeling approaches to incorporate changes in longer-term secondary health outcomes (e.g., stroke, acute myocardial infarction) on healthcare costs.

## **6.2 Rationale for Study Design**

### **6.2.1 Choice of Primary Outcome**

Referral rates of eligible patients was chosen as our primary outcome because we wish to: 1) specifically examine clinic-community linkages for which the referral is the linchpin, and 2) on evaluating the implementation of a PA referral pathway integrated within a health system. The ultimate indicator of provider-patient ‘engagement’ in the clinic setting is the delivery of a complete and accurate EIMG referral to eligible patients. We considered examining patient engagement in the evidence-informed PA program, but this occurs further downstream, involving several additional steps on the periphery and outside of the healthcare setting. However, as part of a secondary aim (effectiveness of the evidence-informed PA program), we will examine patient enrollment rates and factors influencing their decisions (i.e., barriers and facilitators).

### **6.2.2 Study Population**

Our study population will consist of: 1) clinic staff at participating Prisma Health primary care clinics, and 2) all patients eligible to receive an EIMG referral to participate in the evidence-informed PA program at local community PA facilities.

### **6.2.3 Inclusion of Women**

We expect that approximately equal numbers of men and women will be eligible to receive an EIMG referral and have the opportunity to participate in the study. We therefore might expect to enroll women at a similar (or greater) proportion as they appear in the underlying population of ambulatory care. However, in our previous work involving EIMG, women received a greater proportion of referrals (75%) and participated in the PA program at a greater rate (81% to 19%) than men. Therefore, we expect to see levels of participation in the study that reflect these past trends.

Patients that are pregnant are not eligible for participation in EIMG and, therefore, will not be eligible to participate in the study. The PA program is designed for patients with chronic diseases and are not tailored for the specific needs and considerations of pregnant women. A future goal of EIMG, beyond the scope of this study, is to develop, offer, and test an EIMG model specifically tailored for pregnant women and other higher risk populations.

### **6.2.4 Inclusion of Minorities**

This study focuses on the identification of physically inactive patients with chronic disease and their referral to the PA program. The study will include patients regardless of their race, ethnicity, or any other underrepresented status. Conducting the study in Prisma Health primary care clinics, a major health system serving a large and diverse population in Greenville, South Carolina, ensures that we will have a high representation of minority patients. Based on the current patient population served by Prisma Health, we anticipate that approximately 25% of the study participants will be African American, 62% will be White, and approximately 8% will be Hispanic/Latino. It is our intention to pay particular attention to issues of health equity across all dimensions of the study, examining determinants and contextual factors that may potentially impact the participation of vulnerable populations at any point in the EIMG model.

### **6.2.5 Selection of Eligible Prisma Health Primary Care Clinics**

We elected to use the clinic as the unit of observation, rather than individual providers or patients within a clinic. Clustering is preferred when the target of an intervention is a collective or system rather than a particular person or patient, allowing us to evaluate a new standard of care or practice-wide change that may affect patient outcomes. Further, the use of clusters (at the clinic level) reduces potential contamination between groups as patients within a clinic are more likely to be treated similarly and exhibit similar outcomes. Our unit of analysis will be a

compilation of provider-level metrics, aggregated across all providers within a clinic. The negative to clustering at the clinic level includes requiring more participants to obtain equivalent statistical power, more complex analyses, and not being able to blind groups.

### **6.2.6 Selection of Primary Care Settings**

The primary care setting, as opposed to acute and urgent care centers or specialty clinics, was selected for this study as most patient contacts originate and end in primary care. In many cases, primary care is the only place that individuals have access to care. The primary care setting is the cornerstone of health systems in meeting the broader needs of patients, families, and communities. Primary care practices are tasked with providing high quality care for patients on a long-term basis, many of them with co-morbid conditions that are all positively impacted by greater PA levels. The primary care setting is the first point of contact for patient populations (inactive, with diabetes, hypertension, obesity, and dyslipidemia) requiring primary and/or secondary disease prevention, such as PA promotion and counseling. Further, the primary care setting allows for the ongoing observation of the trajectory of chronic diseases through multiple visits over time. Lastly, the patients seen in primary care settings are representative of the surrounding population, allowing for a greater examination of interventions that reduce health disparities and improve health equity.

### **6.2.7 Rationale for Control Condition**

The selection of our control group was influenced by several factors. There are currently only 20 Prisma Health primary care clinics that have not received EIMG onboarding and activation and that are within 15 miles or less of a participating community PA facility. There are no other equivalent Prisma Health primary care clinics to serve as matched controls (i.e., via a stepped wedge design). We are then left with two groups of clinics to serve as controls. The first of these is using a within-clinic design and comparing patient health outcomes before and after the dissemination of the initial EIMG Instructional Video. Secondly, from past experiences, we anticipate that several of the 20 clinics will choose not to adopt EIMG and/or will be non-responsive to our invitation. As one of our study aims, we will evaluate contextual factors and differences between adopting and non-adopting clinics. Clinics that do not adopt EIMG will not be 'activated' and can therefore serve as control clinics, particularly when evaluating patient-level outcomes, as none of their patients will have had the opportunity to participate in EIMG.

## 7.0 STUDY POPULATION

### 7.1 Prisma Health - Clinic Eligibility

As the unit of randomization, we will offer the opportunity to adopt EIMG to 20 Prisma Health primary care clinics that have not yet implemented EIMG. The department chairs for Internal and Family Medicine (Drs. [name] and [name]) have provided their support for EIMG expansion across these primary care clinics.

Eligibility criteria for clinics to participate in this study include the following:

- Prisma Health primary care clinics (i.e., family or internal medicine) located in the Upstate of South Carolina
- Have not received EIMG onboarding or activation in the past;
- Consist of at least two attending providers;
- Be located 15 miles or less from a participating community PA facility.

All potentially eligible Prisma Health primary care clinics were geographically coded to determine the distance to the nearest participating community PA facility. Clinics >15 miles will be ineligible for study participation as previous research consistently demonstrates that engagement in leisure time PA and enrollment in fitness centers is negatively correlated with distance to PA destinations.

### 7.2 Prisma Health – Patient Eligibility

Adult patients (≥18 years of age) will be deemed eligible for the study through two different approaches. First, patient eligibility to receive an EIMG referral is determined in real time through a series of steps that are integrated within the patient workflow process in the Prisma Health primary care clinics. Patients that receive an EIMG referral will have the opportunity to enroll in the community-based PA programs and will be considered as the numerator in our ‘reach’ calculations. Second, all patients that were eligible for an EIMG referral (whether they received one or not) at participating clinics will be identified through a retrospective data extraction process from the Prisma Health EHR that will occur at the end of the study period (end of month 8). These broader sample of patients that were eligible for an EIMG referral will be considered as the denominator in our ‘reach’ calculations.

### 7.3 Patient Eligibility – Participating in the PA Program

Healthcare providers at participating Prisma Health primary care clinics that adopt EIMG will have the ability to identify eligible patients and provide them with an EIMG referral during the patient visit through a process embedded in the patient care workflow at each clinic.

The first step in determining patient eligibility to receive an EIMG referral will involve identifying potentially eligible patients that would benefit the most from participating in an exercise training program. As part of EIMG adoption (both with the EIMG Instructional Video [phase I] and the EIMG Onboard Training [phase II]), clinicians will be guided to identify and refer patients with low physical activity levels with or without any of the following: overweight/obesity, high blood sugar, high blood pressure, or dyslipidemia. Although the provision of referrals is left to the judgement of each clinician, general guidelines for referring patients will be as follows:

- >150 minutes per week of moderate intensity PA (as determined by the PAVS)
- BMI ≥30kg/m^2
- Impaired fasting glucose
- Prediabetes
- Types 2 diabetes mellitus
- Essential hypertension
- Dyslipidemia (including hyperlipidemia, hypertriglyceridemia, hypercholesteremia)

Once a clinician has deemed that a patient would benefit from participating in EIMG, to complete the referral process they will be asked to:

- i. Complete a Risk Severity Assessment to ensure that participating in an exercise training program will be safe and that it is appropriate for their patients;
- ii. Upload the consent and release of information forms signed by the patient (these forms allow the transfer of a limited amount of HIPAA-protected patient health information to the site coordinator at the community PA facility).

This information is electronically sent to a member of the EIMG Referral Team, who checks for completeness and ensures patient eligibility to participate in the PA program. EIMG Referral Team members will contact referring clinicians if any required information is missing or to clarify any safety concerns.

*The final number of patients referred to the EIMG Referral Team will serve as the ‘numerator’ in our Reach calculations (see 13.2 and 13.3).*

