### 4.2 Patient Eligibility

Patients are eligible to participate in EIMG if they are between the ages of 18-80, physically inactive (<150 minutes per week of moderate intensity aerobic activity) and with or without a chronic condition (i.e., overweight/obese, hypertension, type 2 diabetes) that is positively impacted by PA. Patients with uncontrolled hypertension or diabetes, and those at increased fall risk are ineligible to participate in EIMG until symptoms are controlled and physician approval is provided.

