### 4.3 EIMG Clinic Workflow

The EIMG Clinician Decision Modules are incorporated into the EHR as part of clinical workflow. The three Decision Modules include: 1) PA assessment, 2) PA prescription (through patient order sets), and 3) referral to a community PA facility.

**Module 1: PA Assessment.** Front office or nursing staff capture the patient's current PA behavior via the PAVS programmed into the EHR. The PAVS consists of two questions (“how many minutes per day do you exercise?” and “how many days per week?”) to determine if the patient is meeting national PA guidelines of 150 minutes of moderate intensity aerobic activity a week. The PAVS identifies ‘eligible’ patients, provides a best practice alert (BPA) through the EHR stating that the patient may qualify for EIMG, and prompts providers to discuss lifestyle behavior change.

**Module 2: PA Prescription.** The healthcare provider informs eligible patients about the EIMG program, reviews risks, and provides basic PA and health education by providing them with *EIM Rx for Health* handouts for exercising with chronic disease (e.g., obesity, diabetes, hypertension, peripheral artery disease), developed by experts in the field. The healthcare provider then electronically starts an ‘EIMG Order Set’ leading to the patient referral.

**Module 3: Patient Referral.** Through a series of EHR prompts confirming patient eligibility, the healthcare provider sends a referral to the *EIMG Referral Team*. All aspects of the EHR referral process are electronic, except a paper version of the EIMG Consent to Treat and the Release of Information that the patient must sign (either while in the clinic room or at the checkout counter) in order to continue.

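### Section 7.3 states the activity threshold for referral with the opposite sign to 4.2, and the upper age limit of 80 in 4.2 is missing from the synopsis, 7.2, 13.2 and the 7.4 denominator

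*Combined protocol and SAP*

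**What the plan says.** **Activity.** Section 4.2, on who may enter EIMG, requires the patient to be "physically inactive (<150 minutes per week of moderate intensity aerobic activity". Section 7.3 covers whom clinicians at the study clinics should refer. It begins by saying that "clinicians will be guided to identify and refer patients with low physical activity levels", whether or not a cardiometabolic condition is present. The first bullet of the list that follows reads ">150 minutes per week of moderate intensity PA (as determined by the PAVS". The other six bullets are a BMI threshold and diagnoses. The section ties this guidance to both the Instructional Video and the Onboard Training, presents it as general, and leaves the decision to the clinician.

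**Age.** Section 4.2: "Patients are eligible to participate in EIMG if they are between the ages of 18-80". Section 7.2: "Adult patients (≥18 years of age) will be deemed eligible for the study". The synopsis also starts at 18 with no upper limit. The exclusion list in 13.2, which the provider sees on opening the order set, removes only patients under 18.

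**Counting.** The primary outcome is the referral rate among eligible patients. Under 7.3 the numerator is the final number of patients referred to the EIMG Referral Team. Under 7.4 and Appendix A the denominator is pulled retrospectively from the EHR: patients with an inclusion ICD-10 code, less those with an exclusion code. No age limit is stated for that query.

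**The concern.** The text that tells clinicians whom to refer gives the activity criterion in the opposite direction to the program's own entry rule. Because 4.2 and 7.3 both admit patients with or without a chronic condition, activity level is the one criterion meant to apply to every candidate. Followed literally, the bullet would point clinicians to patients who already exceed the guideline.

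The age conflict raises a different problem. Numerator and denominator come from different processes: a real-time referral checked by the Referral Team, and a later ICD-10 query. If one applies an upper age limit and the other does not, the rate is computed over patients who had no chance of being referred.

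**Working it through.** No figure in the plan has to be reproduced for this point. The check sets the statements side by side and then sizes the age effect under a stated assumption.

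**1. Activity: which statement stands alone?**

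| Place | Direction |
|---|---|
| 4.2 | below 150 minutes per week |
| 7.3, sentence introducing the list | low activity |
| 7.3, first bullet | above 150 minutes per week |
| 6.1 | inactive: "All providers at the clinic will have the ability to screen and identify physically inactive patients and provide them with an EIMG referral" |
| 6.2.4 | inactive patients with chronic disease |
| 7.4 | inactive and/or with a listed condition |
| Appendix A | a physical inactivity category, including sedentary lifestyle |

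Section 4.3 prints no inequality. It says that the PAVS is used to "determine if the patient is meeting national PA guidelines of 150 minutes of moderate intensity aerobic activity a week" and that it flags eligible patients, which fits the inactive reading. The 7.3 bullet is the only statement in the other direction, and it conflicts with its own lead-in. A fault in reading the PDF cannot be fully excluded, but it is unlikely: the sign in 4.2 and the BMI sign in the same 7.3 list came through intact.

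**2. Where can the activity sign act?** The numerator depends on whom clinicians refer, so misdirected guidance could change it. The denominator in 7.4 uses ICD-10 codes and no PAVS minutes, so neither sign enters it.

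**3. Where can the age rule act?** Sections 4.4, 7.3 and 13.3 have the Referral Team or Care Coordinator confirm eligibility, but none says whether 18-80 or 18 and over is applied. There are three cases:

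- No cap at referral and none in the query: numerator and denominator match, and 4.2 is not being followed.
- Cap in both: they match, and the synopsis, 7.2 and 13.2 are incomplete.
- Cap at referral but not in the query: they do not match.

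**4. Size of the third case.** Let R be the reach among patients aged 18-80, N the denominator, and f the share of N older than 80.

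Observed reach = R × N(1 − f) / N = R(1 − f)

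R = 0.04 is the planning referral rate at month 8 in 12.3. The documents do not give f; 5% to 15% is assumed.

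- f = 0.05: 0.04 × 0.95 = 0.038, or 3.8%
- f = 0.15: 0.04 × 0.85 = 0.034, or 3.4%

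**5. Effect on the phase comparison.** If f is the same in both phases, the difference becomes (1 − f)(R₂ − R₁) and the ratio R₂/R₁ is unchanged. The contrast shrinks slightly, and no phase effect is created.

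**6. Traceability.** Section 7.4 says that the ICD-10 list rests on criteria in section 7.2.1, which does not exist in the current text. The list therefore cannot be traced to one of the conflicting statements.

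**The case against.** The best defense is that this is a typing error that will mislead few people. The lead-in to the list says the opposite, every related section describes inactive patients, and the list is general guidance subject to clinical judgment. Section 4.1 places the PAVS and alert work in the EHR from 2016 onward, before this study, and eligibility is checked again after referral. On age, section 4 describes the existing program, which 14.1 places outside the research, while the synopsis, 7.2 and 13.2 agree with one another.

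Much of this stands, and it limits the severity. It does not remove the contradiction. Section 7.3 is operative text, conveyed through the two exposures that the study compares. Section 6.2.2 defines the patient population as those eligible for an EIMG referral, and the same program receives the referrals, so its age limit cannot be set aside as background.

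Three stronger readings are tempting and not supported:

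- A reader might infer that the sign also corrupts the denominator. It does not, because the denominator contains no activity minutes.
- A reader might infer that 4.2 and 7.3 divide patients into two complementary groups. The two activity statements are mutually exclusive, but a patient at exactly 150 minutes meets neither. The seven bullets are also not joined by a stated AND or OR: read as alternatives, a patient with hypertension meets 7.3 at any activity level.
- A reader might infer that the training or the EHR alert already applies the reversed threshold. No section shows this.

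**Conclusion.** Both contradictions are present in the current text. The activity bullet in 7.3 is wrong as written and appears to be a reversed sign. Its reach is the referral guidance and, potentially, the numerator of the primary outcome; its size cannot be estimated from the documents. The age conflict leaves the handling of patients over 80 undefined. It lowers the reported rate only if the cap is applied at referral and not in the denominator query. In that case the relative loss equals the share over 80, and an assumed 5% to 15% gives 3.8% to 3.4% in place of 4%. With a stable age mix, the video-versus-training comparison is scaled by the same factor and is not otherwise distorted. The severity is minor.

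**What to change.** Reconcile the synopsis, 4.2, 7.2, 7.3 and 13.2 to one activity threshold and one age rule. The sponsor's clinicians should decide which statements stand. Then:

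- apply the same age rule in the referral order set, the Referral Team check and the 7.4 denominator query;
- check that the Instructional Video, the Onboard Training material and the EHR alert match the reconciled activity threshold;
- replace the reference to section 7.2.1 in 7.4 with the section that holds the agreed criteria.

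The cost is protocol wording, a check of existing materials and, if an upper age limit is kept, one extra condition in the EHR query. The design, the sample size and the analysis model do not change.
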